4.1.5 Blinding and procedures for unblinding

4.1.5.1 Blinding

Patients, investigators and everyone involved in trial conduct or analysis or with any other interest in this double-blind trial will remain blinded with regard to the randomized treatment assignments until after database lock.

The randomization code will be kept secret by Clinical Trial Support up to database lock.

The randomization codes will be provided to bioanalytics prior to last patient out to allow for the exclusion from the analyses of pharmacokinetic (PK) samples taken from placebo patients. Bioanalytics will not disclose the randomization code or the results of their measurements until the trial is officially unblinded. Serum drug levels and demographic data together with treatment assignments and dosing information may be made available to individuals outside of the trial team for the purpose of PK dataset generation and analysis in accordance with sponsor's standard procedures.

Due to the requirements to report Suspected Unexpected Serious Adverse Reactions (SUSARs), it may be necessary for a representative from BI's drug safety group to access the randomisation code for individual patients during study conduct via the IRT system. In such cases, access to the code will only be permitted by authorised drug safety representatives. Refer to [Section 4.1.5.2](#) for rules of breaking the blinding code for an individual or for all patients in emergency situations

4.1.5.2 Unblinding and breaking the code

Emergency unblinding will be available to the Investigator / Pharmacist / investigational drug storage manager via IRT. It must only be used in an emergency situation when the identity of the trial drug must be known to the Investigator in order to provide appropriate medical treatment or otherwise assure safety of trial participants. The reason for unblinding must be documented in the source documents and/or appropriate CRF page along with the date and the initials of the person who broke the code.

4.1.6 Packaging, labelling, and re-supply

BI 655066, adalimumab, and matching placebo supplies will be provided by Boehringer Ingelheim Pharma GmbH & Co KG, Biberach, Germany (see [Section 4.1.1](#) for more details). Pre-filled syringes of study medication will be provided in individual boxes identified with the trial number, batch and medication number. Supply of study medication will be managed by the IRT.

For details of packaging and the description of the label, refer to the ISF.

4.1.7 Storage conditions

Drug supplies will be kept in their original packaging and in a secure limited access storage area according to the recommended storage conditions on the medication label. A temperature log must be maintained for documentation.

If the storage conditions are found to be outside the specified range, the sponsor must be contacted immediately. Refer to the ISF.

Trial medication must be securely stored, e.g. in a locked refrigerator or at a pharmacy. The medication may only be dispensed to trial patients according to the CTP by authorized personnel as documented in the trial staff list.

4.1.8 Drug accountability

Drug supplies will be provided by the sponsor.

The Investigator and/or Pharmacist and/or investigational drug storage manager will receive the investigational drugs delivered by the Sponsor when the following requirements are fulfilled:

- Approval of the trial protocol by the IRB / ethics committee,
- Availability of a signed and dated clinical trial contract between the Sponsor and the head of the investigational site,
- Approval/notification of the regulatory authority, e.g. competent authority,
- Availability of the curriculum vitae of the principal Investigator,
- Availability of a signed and dated clinical trial protocol
- Availability of the proof of a medical license for the principal Investigator
- Availability of Form 1572 (for USA).

All unused medication must be returned to the sponsor. Used medication will be destroyed per local guidelines. Account must be given for any discrepancies.

Receipt, usage, and return must be documented. Account must be given for any discrepancy. These records will include dates, quantities, batch / serial numbers, expiry ('use- by') dates, and the unique code numbers assigned to the investigational product and trial patients. The Investigator / pharmacist / investigational drug storage manager will maintain records that document adequately that the patients were provided the doses specified by the CTP and reconcile all investigational products received from the Sponsor. At the time of return to the Sponsor and/or appointed CRO, the Investigator / pharmacist / investigational drug storage manager must verify that all unused or partially used drug supplies have been returned by the clinical trial patient and that no remaining supplies are in the Investigator's possession.

4.2 CONCOMITANT THERAPY, RESTRICTIONS, AND RESCUE TREATMENT

4.2.1 Rescue medication, emergency procedures, and additional treatments

There are no special emergency procedures to be followed.

Stable doses of concomitant therapies for chronic conditions, for which neither the condition nor the treatment are judged to exclude the patient from participation (cf. [Section 3.3](#)) are permissible. All concomitant medications should be carefully evaluated by the investigator, and the CML should be contacted when there are questions regarding concomitant medications.

In the event that a patient experiences an intolerable increase of psoriasis, as deemed by the investigator, during the course of the trial the patient will be discontinued from the trial to receive rescue treatment.

In case of adverse events in need of treatment symptomatic therapy according to investigator judgment will be permitted. All concomitant and/or rescue therapies will be recorded on the appropriate pages of the eCRF.

4.2.2 Restrictions

4.2.2.1 Restrictions regarding concomitant treatment

The medications (or classes of medications) listed in [Table 4.2.2.1: 1](#) must not be taken for the time periods as specified.

Table 4.2.2.1: 1 Restricted medications

Medication or class of medications	Restriction duration (through EOO Visit)
Guselkumab, tildrakizumab	Not allowed neither before nor during trial participation
Briakinumab, secukinumab (Cosentyx®), ustekinumab (Stelara®)	6 months prior to randomisation
Brodalumab, ixekizumab	4 months prior to randomisation
Infliximab (Remicade®) Investigational products for psoriasis (non biologics)	12 weeks prior to randomisation
Etanercept (Enbrel®) Live virus vaccinations	6 weeks prior to randomization

Table 4.2.2.1: 1 Restricted medications (cont'd)

Medication or class of medications	Restriction duration (through EOO Visit)
Any investigational device or product (excludes psoriasis products) Other systemic immunomodulating treatments, e.g. methotrexate, cyclosporine A, corticosteroids ¹ , cyclophosphamide, tofacitinib (Xeljanz [®]), apremilast (Otezla [®]) Other systemic psoriasis treatments (e.g. retinoids, fumarates, any other drug known to possibly benefit psoriasis) Photochemotherapy (e.g., PUVA)	30 days prior to randomisation
Phototherapy (e.g., UVA, UVB) Topical treatment for psoriasis or any other skin condition (e.g. corticosteroids ² , vitamin D analogues, vitamin A analogues, pimecrolimus, retinoids, salicylvaseline, salicylic acid, lactic acid, tacrolimus, tar, urea, andanthralin, α -hydroxy, fruit acids)	14 days prior to randomisation

¹ No restriction on corticosteroids with only a topical effect (e.g. inhalative corticosteroids to treat asthma or corticosteroid drops used in the eye or ear).

² Exception: Topical steroids of US class 6 (mild, such as desonide) or US class 7 (least potent, such as hydrocortisone) for use on the face, axilla, and/or genitalia with a restriction of use within 24 hours prior to trial visit in which PASI is assessed.

4.2.2.2 Restrictions on diet and life style

Patients should be fasted for at least 8 hours prior to collection of the safety laboratory samples, starting from Visit 2. Moisturizers/emollients containing retinoids and the use of tanning beds are not allowed during the study.

4.2.2.3 Restrictions regarding women of childbearing potential

Female patients of childbearing potential should use the contraception methods described in [Section 3.3.2](#) and the patient information.

4.3 TREATMENT COMPLIANCE

Study medication will be administered in accordance with the protocol. At Visit 2 (randomisation) the study drugs will be administered by authorized study personnel (e.g. study nurse). At Visits 3 and 4 the adalimumab (active or placebo) injections will be self-administered by the patient under supervision of study personnel. Any further adalimumab administrations (active or placebo) will be self-administered by the patient at home. BI 655066 (active or placebo) will be self-administered by the patient under supervision of the

study personnel at Visit 5 (Week 4) and at any later visit with BI 655066 (active or placebo) administration.

The measured plasma concentrations will provide additional information about compliance. Any missed dose has to be documented. The study site should remind the patient by phone about the adalimumab (active or placebo) injections to be self-administered by the patient at home. The patient will record date and time of each home administration in a paper diary.

5. VARIABLES AND THEIR ASSESSMENT

5.1 TRIAL ENDPOINTS

None of the primary and secondary endpoints are considered safety issues.

5.1.1 Primary Endpoint(s)

There are co-primary endpoints to assess the efficacy of BI 655066 for the treatment of moderate to severe chronic plaque psoriasis. These are as follows:

- Achievement of $\geq 90\%$ reduction from baseline PASI score (PASI 90) at Week 16
- Achievement of an sPGA score of clear or almost clear at Week 16

At the trial level, the co-primary endpoints will be the proportion of patients achieving PASI 90 and a sPGA score of clear or almost clear at Week 16 in each of the treatment groups.

5.1.2 Secondary Endpoint(s)

Key Secondary Endpoints:

The key secondary endpoints are as follows:

- Achievement of $\geq 75\%$ reduction from baseline PASI score (PASI 75) at Week 16
- Achievement of 100% reduction from baseline PASI score (PASI 100) at Week 16
- Achievement of $\geq 90\%$ reduction from baseline PASI score (PASI 90) at Week 44 for those patients who are re-randomized at Week 16

Other Secondary Endpoints:

The other secondary endpoints are as follows:

- Achievement of an sPGA score of clear or almost clear (0 or 1) at Week 44
- Achievement of sPGA score of clear (0) at Week 44

5.1.3 Further Endpoints

The further endpoints are as follows:

- Achievement of PASI 50 at all visits collected
- Achievement of PASI 75 at all visits collected
- Achievement of PASI 90 at all visits collected
- Achievement of PASI 100 at all visits collected
- Time until the first achievement of PASI 50, PASI 75, PASI 90, PASI 100 and sPGA 0 or 1
- Time until loss of PASI 75, PASI 90, PASI 100 and sPGA 0 or 1 response

- Change and percent change from baseline in PASI at all visits collected
- Absolute PASI score of <3 at all visits collected
- Achievement of an sPGA score of clear or almost clear at all visits collected
- Achievement of an sPGA score of clear at all visits collected
- Change from baseline in DLQI at all visits collected
- Achievement of a DLQI score of 0 or 1 at all visits collected
- Achievement of a reduction of 5 or more points from baseline in DLQI score at all visits collected
- Change from baseline in WLQ at all visits collected
- Change and percent change from baseline in Nail Psoriasis Severity Index (NAPSI) at all visits collected
- Change and percent change from baseline in Palmoplantar Psoriasis Severity Index (PPASI) at all visits collected
- Change and percent change from baseline in Psoriasis Scalp Severity Index (PSSI) at all visits collected
- Response to individual questions on the self-administration questionnaire at each visit where BI 655066 active or placebo is self-administered
- Change of metabolic risk factors from baseline (waist circumference, body weight, HOMA-index)

5.2 ASSESSMENT OF EFFICACY

- The skin condition will be assessed by using the PASI, sPGA, and other relevant scores as described in [section 5.1.1](#) and the ISF.
- Symptoms, quality of life, and physical function will be assessed by the DLQI and the WLQ.

Details of the efficacy assessments are listed in the Appendix ([Section 10](#)).

5.3 ASSESSMENT OF SAFETY

Safety will be assessed descriptively based on:

- Adverse events
- Serious adverse events
- Clinical laboratory values (haematology, clinical chemistry and urinalysis)
- Intensity of adverse events assessed by Rheumatology Common Toxicity Criteria (RCTC) version 2.0 (refer to ISF for details).
- Physical examination
- Vital signs
- 12-lead ECG
- Local tolerability

5.3.1 Physical examination

Complete and target physical examinations will be performed at visits as described in the [flow chart](#). Complete physical examination will include vital sign assessment and general appearance as well as evaluation of all relevant organ systems. Targeted physical examination will include vital sign assessment and evaluation of organ systems associated with AE(s) symptoms or laboratory abnormalities.

Clinically relevant abnormal findings will be reported as baseline conditions or AEs.

5.3.1.1 Waist circumference

Waist circumference measurements should be made around a patient's bare midriff, after the patient exhales while standing without shoes and with both feet touching and arms hanging freely. The tape should be placed perpendicular to the long axis of the body and horizontal to the floor and applied with sufficient tension to conform to the measurement surface. Waist circumference should be determined by measuring the midpoint between the lowest rib and the iliac crest.

5.3.1.2 Body weight

Body weight measurements should be done on the same scale for each patient. In order to get comparable body weight values, body weight measurements should be performed in the following way:

- fasting (except for the Screening Visit)
- after the urine sampling (body weight after bladder voiding)
- shoes and coat/jackets should be taken off
- pockets should be emptied of heavy objects (i.e. keys, coins etc)

5.3.2 Vital Signs

Vital signs evaluations will be performed at visits as shown in the [flow chart](#). This includes temperature, pulse rate, systolic/diastolic blood pressure and respiratory rate. Respiratory rate, pulse rate, and blood pressure will be measured after patients have been sitting comfortably for at least five minutes. Measurement of vital signs should precede blood sampling to avoid the impact of blood sampling on the vital measurements. At dosing visits vital signs evaluations will be performed pre-dose and at Visit 2 and Visit 5 additional measurements will be performed approximately 5 minutes post-dose (5 min. after last injection) and approximately 60 minutes post-dose (60 min. after last injection).

Patients should be closely monitored for signs and symptoms of hypersensitivity reactions for approximately 2 hours after the last injection at the Randomization Visit and for approximately 1 hour after the last injection at all other visits with drug administration. Hypersensitivity reactions should be treated according to medical standards. Pre-medications for further injections might be considered and will be agreed on between investigator and BI clinical monitor.

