4.1.4 Drug assignment and administration of doses for each patient

An IRT will be used to allocate medication to patients through medication numbers. At visits where study medication is to be administered or to be dispensed to patients, study sites will be required to complete the medication resupply module in the IRT. These visits are specified in the [Flow Chart](#), see also [Fig. 3.1: 1](#))

At randomization as well as subsequent medication dispense visits, IRT will assign medication numbers. Site personnel will enter the medication numbers in the eCRF.

Study drugs will be administered subcutaneously. Injections will be given in a double blind/dummy fashion with each patient receiving 2 injections of BI 655066 or matching placebo and 1 injection (2 injections only at randomisation) of comparator drug adalimumab or matching placebo. Adalimumab will be dosed and administered according to the prescribing information with a loading dose of 80mg at randomisation followed by a dose of 40mg at Week 1 and a dose of 40mg at every other week.

At Visit 2 (randomisation) study medication (2 injections BI 655066 or placebo and 2 injections adalimumab or placebo) will be administered by the investigator or authorized study personnel. It does not matter whether BI 655066 or adalimumab (active or placebo) will be administered first at Visit 2. The four injections should be administered within approximately 5 minutes.

At Visits 3 and 4 (Weeks 1 and 3) study medication (1 injection adalimumab or placebo) will be self-administered by the patient at the study site under supervision of study personnel. All

following adalimumab (active or placebo) injections (at weeks 5, 7, 9, 11, etc. with a time window of ± 3 days) will be self-administered by the patient at home. The study site should remind the patient by phone when each home administration is due. The patient is asked to record date and time of each home administration of adalimumab (active or placebo) in a paper diary.

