6.2.2 Treatment period

The treatment period is from Visit 2 to End of Treatment (EOT) Visit.

Safety laboratory testing

Visits 2, 5, 8, 11, EOT and EOO should be performed in fasted state (8 hours no food and only water). This is not necessary at the Screening Visit. If a patient comes in non-fasted where a fasting condition is required, the visit should be performed, the non-fasted condition documented on the laboratory requisition, and the patient reminded about the expected conditions.

Pregnancy testing

Urine pregnancy testing for all woman of child-bearing potential will be conducted on-site approximately every four weeks and must be negative to further treat the patient. The pregnancy testing should be done prior to administration of study drug. A positive urine test must be confirmed with a serum pregnancy test.

Randomization via IRT and administration of study medication should be the last activity at Visit 2.

Skin biopsies should be collected prior to administration of study drug at dosing visits.

Venipuncture (i.e. safety laboratories, PK, ADA, biomarkers) should be the last procedure prior to any study drug administration. On dosing visits PK and ADA samples should be taken approximately within 1 hour prior to administration of study drug.

Patients should be closely monitored for signs and symptoms of hypersensitivity reactions for approximately 2 hours after the last injection at the Randomization Visit (Visit 2) and approximately 1 hour after the last injection at all other drug administration.

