11.0 Safety Analysis

11.1 General Considerations

Safety analyses will include adverse events, laboratory, local tolerability, ECG, and vital sign measurements. Safety summaries will be provided using the safety population in each period as defined in Section 5.1. Comparison between risankizumab group and adalimumab group will be performed in the Safety Population in Safety_A and Safety_B_RR populations. Continuous variables will be analyzed using one-way ANOVA and categorical variables will be analyzed using Fisher's exact test. For the analyses of AEs, only P values ≤ 0.100 when rounded to three digits will be presented.

Missing safety data will not be imputed.

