Adjudicated CV Events (continued)	Other CV events	Adjudicated events	Display underlined terms defined by the following adjudicated terms: 
 • Thrombotic events which includes CETERM values: Deep Vein Thrombosis, TIA, Pulmonary Embolism, Non-fatal Non-Cardiac/Non-Neurological Arterial Thrombosis/ Thromboembolism, Other Venous Thrombosis, specified (non-fatal) • Cardiac arrhythmia which includes CETERM of: Clinically Significant Arrhythmia • Congestive heart failure which includes CETERM of Heart Failure • Hypertensive emergency 	N
Serious infections, TB, fungal and opportunistic infections (including herpes zoster)	Serious infections	Serious PTs of the CMQ (company MedDRA query) Infections (CMQ 8000018)	PTs	Y
	TB	Tuberculosis (including Investigations) CMQ (code 80000033)	PTs	Y
	Opportunistic infections	Opportunistic infections CMQ (code 80000073)	PTs	N

Table 21. Areas of Safety Interest (Continued)

ASI Grouping	Categories (ASI)	Search Criteria	Terms to Display	Include in AE Overview (Y/N)
Serious infections, TB, fungal and opportunistic infections (including herpes zoster) (continued)	Fungal infections	Fungal infections CMQ (code 80000063)	PTs	N
	Herpes Zoster	Herpes zoster CMQ (code 80000175)	PTs	N
Malignancies	All possible malignancies	Narrow – Malignancies (SMQ 20000090)	PTs	N
	Malignant Tumours	Narrow – Malignant tumours (SMQ 20000194)	PTs	Y
	Non-melanoma skin cancer (NMSC)	Broad – Skin malignant tumours (SMQ 20000204) excluding terms identified by the Melanoma CMQ (code 80000119)	PTs	N
	Malignant Tumours excluding NMSC	'Malignant Tumours excluding NMSC' is identified by the 'Malignant Tumours' search excluding terms identified by the 'Non-melanoma skin cancer' (NMSC) search.	PTs	Y
Hypersensitivity Reaction	Hypersensitivity	Narrow – Hypersensitivity (SMQ 20000214)	PTs	Y – serious events only

Table 21. Areas of Safety Interest (Continued)

ASI Grouping	Categories (ASI)	Search Criteria	Terms to Display	Include in AE Overview (Y/N)
Hypersensitivity Reaction (continued)	Anaphylactic Reaction	Narrow – Anaphylactic reaction (SMQ 20000021)	PTs	N

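### On-site observation for acute reactions follows every active risankizumab dose but few active adalimumab doses, so non-serious hypersensitivity events are ascertained unequally

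*Protocol*

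**What the plan says.** Protocol 5.3.2 and flow-chart footnote 4 set observation for hypersensitivity "for approximately 2 hours after the last injection at the Randomization Visit" and then "for approximately 1 hour after the last injection at all other visits with drug administration". Section 5.3.2 also adds post-dose vital signs: "at Visit 2 and Visit 5 additional measurements will be performed approximately 5 minutes post-dose", and again at about 60 minutes.

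The place of dosing differs by drug. All injections of risankizumab or its placebo are given at the site (Protocol 4.1.4, flow-chart footnote 15). Adalimumab or its placebo is given on site at Weeks 0, 1 and 3. After that it "will be self-administered by the patient at home. The study site should remind the patient by phone when each home administration is due". For these home doses, Protocol 4.3 says: "The patient will record date and time of each home administration in a paper diary". No symptom entry or reaction query is described.

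Protocol 6.2.2 words the monitoring rule differently: "approximately 1 hour after the last injection at all other drug administration", with no mention of visits.

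SAP 11.1 states: "Comparison between risankizumab group and adalimumab group will be performed in the Safety Population in Safety_A and Safety_B_RR populations". Categorical safety variables are compared by Fisher's exact test, and AE p-values are shown if 0.100 or below. SAP Table 21 lists hypersensitivity and anaphylactic reaction as areas of safety interest; only serious hypersensitivity events enter the AE overview. Protocol 7.3.4 describes safety analysis as descriptive, without hypothesis tests.

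**The concern.** The double dummy gives both arms the same procedures, which protects the blind. It does not equalise what is being observed. After Week 3, each observation period in a patient on adalimumab follows a placebo injection, while the active doses are taken at home. In a patient on risankizumab, each active dose is followed by staff observation. The extra vital signs at Visit 5 show the same pattern, because only risankizumab or its placebo is injected there.

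A mild systemic reaction that starts and resolves within the hour will be seen by staff after active risankizumab. After a home adalimumab dose it must be remembered and volunteered later. The between-arm comparison of non-serious acute reactions then mixes a drug difference with a difference in how closely the active dose was watched, and neither document mentions this. The mixing is most complete in Safety_B_RR, where no active adalimumab dose is observed.

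**Working it through.** **1. Active dosing occasions by place** (Protocol Table 4.1.4: 2; flow-chart footnotes 15 and 17).

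| Comparison | Drug | Active occasions (weeks) | On site | At home |
|---|---|---|---|---|
| Part A | risankizumab | 0, 4 | 2 of 2 | 0 |
| Part A | adalimumab | 0, 1, 3; 5, 7, 9, 11, 13, 15 | 3 of 9 | 6 of 9 (67%) |
| Part B, re-randomised | risankizumab | 16, 20, 32 | 3 of 3 | 0 |
| Part B, re-randomised | adalimumab | 17 to 41, every 2 weeks | 0 of 13 | 13 of 13 (100%) |

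Over Weeks 0 to 41, 19 of 22 active adalimumab occasions (86%) are at home.

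**2. Time from a home dose to the next AE visit.** Visits fall every 4 weeks from Week 4. A dose at Week 5 is followed by the Week 8 visit (21 days) and a dose at Week 7 by the same visit (7 days). The pattern repeats to Week 41. Ten home doses lie 21 days before the next visit and nine lie 7 days before: (10 × 21 + 9 × 7)/19 = 273/19 = 14.4 days on average.

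The gap concerns only reactions inside the observed hour or two. Later-onset reactions depend on recall for both drugs. The next visit after a risankizumab dose at Week 4, 16, 20 or 32 is 28 days away, so later-onset reactions give adalimumab no disadvantage.

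**3. Illustration of size.** Let r be the chance that a home reaction is captured, relative to an on-site one. The documents give no value, so r is an assumption shown over a range. Assume also equal reaction risk per occasion, full capture on site, and rare events.

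Share of adalimumab reactions captured: Part A (3 + 6r)/9; Part B 13r/13 = r. The distortion of the risankizumab-to-adalimumab ratio is the inverse of that share.

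| r | Part A captured | Part A distortion | Part B captured | Part B distortion |
|---|---|---|---|---|
| 0.25 | 4.5/9 = 50% | 2.00 | 25% | 4.00 |
| 0.50 | 6/9 = 67% | 1.50 | 50% | 2.00 |
| 0.80 | 7.8/9 = 87% | 1.15 | 80% | 1.25 |
| 1.00 | 100% | 1.00 | 100% | 1.00 |

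**4. What a planned table would show.** The SAP tabulates subjects with events and events per 100 patient-years, not events per dose. Under the same assumptions, the ratio per patient is about 2/(3 + 6r) in Part A and 3/(13r) in Part B:

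- Part A: 2/9 = 0.22 with full capture, 2/7.8 = 0.26 at r = 0.80, 2/6 = 0.33 at r = 0.50.
- Part B: 3/13 = 0.23 with full capture, 3/10.4 = 0.29 at r = 0.80, 3/6.5 = 0.46 at r = 0.50.

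On these assumptions, under-capture would shrink a difference in favour of risankizumab rather than create an excess.

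**The case against.** The other side has several good arguments.

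- **Home reactions are not lost.** Protocol 5.3.7 requires all AEs to be collected from consent onward, and the flow chart marks AEs at every visit. A reader might infer that home reactions go unrecorded. The documents do not support that: capture is less complete, not absent.
- **Serious events.** These depend little on recall, and they are the only hypersensitivity events in the AE overview.
- **Size.** A reader might take the distortion factors as an apparent risankizumab excess of up to twofold or more. They are per-dose illustrations on an assumed r and correspond to no planned table. If reactions cluster at first exposure, the Part A effect is smaller, because the first three adalimumab occasions are observed.
- **Local reactions.** A reader might extend the point to injection-site reactions. These have their own investigator check, done pre-dose at scheduled visits (Protocol 5.3.5, SAP 11.6). Its timing tends to favour finding adalimumab reactions: at Week 16 the last active adalimumab dose was 1 week earlier (Week 15), against 12 weeks for risankizumab (Week 4). In re-randomised patients the gaps are 1 against 8 weeks at Week 28, and 3 against 12 at Week 44.
- **Protocol 6.2.2.** A reader might see a requirement to monitor home doses. Section 6.2 concerns procedures at selected visits, and the amendment log describes the edit as applying to dosing visits, so this may be loose wording. The texts still differ and need reconciling.
- **Procedures are identical and blinded, and the protocol calls safety descriptive.** This is true, but the SAP does plan a tested between-arm comparison, and identical procedures do not give equal observation of the active drugs.

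The dose counts, the content of the diary and the silence of both documents on the difference all stand.

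**Conclusion.** The point holds in a limited form. On-site observation follows all active risankizumab occasions (2 of 2 and 3 of 3) but only 3 of 9 active adalimumab occasions in Part A and 0 of 13 in re-randomised Part B. Acute, non-serious systemic reactions after home doses depend on recall 1 or 3 weeks later. The comparisons of non-serious hypersensitivity and anaphylactic-reaction events in Safety_A, and above all in Safety_B_RR, are therefore ascertained unequally.

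The likely direction is under-counting of adalimumab reactions, to the relative disadvantage of risankizumab. This assumes that recall misses some reactions that staff would have seen. The size is unknown, because the documents give neither reaction rates nor any measure of recall. The point does not reach AE collection in general, serious events or local injection-site reactions, and it has no bearing on the efficacy conclusions. It is a cheap improvement, not a flaw that threatens the trial.

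**What to change.** 1. **Diary.** Add one line to the existing paper diary: any reaction after this injection (yes or no), symptoms, onset time. Use it in both arms and after every injection, at site or at home, active or placebo. A line for home doses only would prompt for active adalimumab but never for active risankizumab. Sites review it at the next visit and enter reactions as AEs.
2. **SAP 11.2.1.** Add one table of treatment-emergent hypersensitivity and anaphylactic-reaction events by arm, by most recent injection (drug, active or placebo, site or home) and by time since that injection. Place alone is not enough: after Week 3, site injections in patients on adalimumab are placebo, and home injections in patients on risankizumab are placebo. Label the between-arm comparison of non-serious acute reactions as unequally observed, especially in Safety_B_RR. Do not rest the between-arm statement on Visit 2 alone, because all Safety_B_RR patients were assigned adalimumab then.
3. **Protocol wording.** Reconcile 6.2.2 with 5.3.2, flow-chart footnote 4 and 4.1.4 on which administrations the monitoring covers. This review takes no position on which text should prevail.

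The cost is one diary field, a little extra site review and one programmed table, with no added visits or staff. Prompting will raise the number of mild reaction reports in both arms. If the diary can no longer be changed, the table and label need no new procedure and can be added before the SAP is signed off, which SAP 3.0 places before database lock.
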